5.5.3 Follow-up of AEs and SAEs

After the initial AE/SAE report, the Investigator will proactively follow each participant at subsequent visits/contacts. All SAEs will be followed until resolution, stabilization, the event is otherwise explained, or the participant is lost to follow-up, or until the trial is concluded.

5.5.4 Regulatory Reporting Requirements for SAEs

It will be clearly communicated to participating investigators that the trial does not replace the reporting of AEs/SAEs that should occur as part of routine practice as specified by local regulations. It is not the intention of the trial to influence or change the usual local reporting processes. Investigators should continue to report any AEs/SAEs they would typically report using the mechanisms routinely used in their healthcare practice. Therefore, although the data collected for this trial are primarily safety-related data, reporting mechanisms of AEs to regulatory authorities should not be altered and are to continue according to local standards.

If an investigator (or designee) becomes aware that a trial participant has experienced a SAE within 21 days post-vaccination, it must be reported to Sponsor using the eCRF and within the timeframes mentioned in below **Table 4**. This is essential for meeting Sponsor legal obligations and ethical responsibilities for participant safety and the safety of a marketed vaccine. The report must be completed as thoroughly as possible, with all available details of the event. The SAE will be linked to the central safety database with a trial ID link mechanism and reporting to Indian regulatory authority will be performed as per their requirement.

For SAEs related to the marketed vaccine, the investigator must always provide an assessment of causality at the time of the initial report.

The Sponsor will comply with country-specific regulatory requirements related to safety reporting to the regulatory authority, institutional review board/independent ethics committee (IRB/IEC), and investigators.

CONFIDENTIAL

Phase IV Clinical Trial Protocol

GlaxoSmithKline
A phase IV trial of *Fluarix Tetra* in Indian
adults aged 65 years and older
Version 2.0, dated: 05 May 2023
Protocol/ Study No.: 218702
Page 47 of 74

Table 4. Timeframes For Submitting SAEs

Type of Event	Initial Reports		Follow-up of Relevant Information on a Previous Report	
	Timeframe	Documents	Timeframe	Documents
SAEs	24 hours	eCRF	14 Calendar days	eCRF, SAE Form, Table 5 as per NDCT Rule 2019 and relevant medical records

eCRF: electronic Case Report Form; SAE: serious adverse event, NDCT: New Drug and Clinical Trials

Backup System in Case the Electronic Reporting System Does Not Work

5.5.5 Pregnancy

Not applicable.

5.5.6 Solicited Adverse Events

AEs that comprise the primary interest of the study are designated as solicited AEs. The list of pre-specified solicited AEs is listed below:

CONFIDENTIAL

Phase IV Clinical Trial Protocol

GlaxoSmithKline
A phase IV trial of *Fluarix Tetra* in Indian
adults aged 65 years and older
Version 2.0, dated: 05 May 2023
Protocol/ Study No.: 218702
Page 48 of 74

Table 5. List of Pre-Specified Solicited AEs

Solicited Administration-site Events
Pain
Redness
Swelling
Solicited Systemic Events
Fever
Headache
Myalgia (Muscle pain)
Arthralgia (Joint pain)
Fatigue
Gastrointestinal symptoms (including nausea, vomiting, diarrhea and/or abdominal pain)
Sweating
Shivering

Body temperature will be recorded preferably in the evening and in case temperature was measured more than once per day, the highest temperature will be recorded in the eCRF.

5.5.7 Disease-related Events and/or Disease-related Outcomes Not Qualifying as Adverse Events or Serious Adverse Events

Not applicable.

5.6 Treatment of Overdose

Not applicable.

5.6.1 Other Measures (If Applicable)

Not applicable.

CONFIDENTIAL

Phase IV Clinical Trial Protocol

GlaxoSmithKline
A phase IV trial of *Fluarix Tetra* in Indian
adults aged 65 years and older
Version 2.0, dated: 05 May 2023
Protocol/ Study No.: 218702
Page 49 of 74

5.7 Data Sources and Collection

A diary card will be provided to trial participants to fill it on a daily basis. The completed diary card will be collected from the participant on Day-22 and data will be captured in the eCRF. A telephone follow-up call will be performed by the Investigator team to assess the participant's health status.

Blood sample collection for immunogenicity data will be collected pre-vaccination at Day 1 and post-vaccination at Day 22. The Investigator team will capture the data in an eCRF. SAEs, if any, will be reported using the SAE Reporting Form.

For safety assessment, vital signs and physical examination data at Day 1 will be assessed and recorded in the eCRF. Solicited AEs up to Day 7, unsolicited AEs up to Day 21 and SAEs up to Day 21 will be recorded in the paper diary card by participant and transcribed into the eCRF.

Table 6. Data Collection Schedule

Visit number	Baseline	Follow-up (Telephonic)	End of Study
Time points	Day 1	Day 8 (+2)	Day 22 (+3)
Informed consent	✓		
Inclusion and exclusion criteria	✓		
Physical examination	✓		
Demographic data	✓		
Medical history	✓		
History of Flu vaccination	✓		
Current medical condition	✓	✓	✓
Concomitant medication	✓	✓	✓
Vital signs	✓		
Data related to sample collection	✓		✓
Telephonic data collection		✓	

CONFIDENTIAL

Phase IV Clinical Trial Protocol

GlaxoSmithKline
A phase IV trial of *Fluarix Tetra* in Indian
adults aged 65 years and older
Version 2.0, dated: 05 May 2023
Protocol/ Study No.: 218702
Page 50 of 74

Visit number	Baseline	Follow-up (Telephonic)	End of Study
Time points	Day 1	Day 8 (+2)	Day 22 (+3)
Diary card data collection			✓
Trial conclusion			✓

5.7.1 Baseline/ Enrollment

The following data will be collected at baseline for all enrolled participants:

- Demographics (age, year of birth, ethnicity, race, and sex)
- Medical history
- History of flu vaccination for last 3 years
- Current medical condition
- Vitals
- Physical examination
- Immunogenicity assessment parameters: GMT, MGI, SCR and SPR

5.7.2 Follow-up

The following data will be collected for all enrolled participants at the telephonic follow-up timepoint:

- Current medical condition
- Any AEs
- Assessment of patient diary card

The following data will be collected in eCRF for all enrolled participants at Day 22 which is end of trial for the participant:

- Current medical condition

CONFIDENTIAL

Phase IV Clinical Trial Protocol

GlaxoSmithKline
A phase IV trial of *Fluarix Tetra* in Indian
adults aged 65 years and older
Version 2.0, dated: 05 May 2023
Protocol/ Study No.: 218702
Page 51 of 74

- Immunogenicity assessment parameters: GMT, MGI, SCR and SPR
- SAEs
- Solicited and unsolicited AEs
- Study conclusion data

5.7.3 Participant Discontinuation/Withdrawal

Refer to [section 5.2.5](#).

6. STATISTICAL METHODS

6.1 Statistical Hypotheses

All analyses will be descriptive. No hypothesis will be tested.

6.2 Sample Size

Approximately 250 participants will be enrolled in this trial to achieve 200 evaluable participants considering that some participants may drop out of the study or some may not be included in data analysis due to missing or invalid data.

Table 7. 95% Clopper-Pearson (exact) Confidence Intervals and Probabilities to Observe at least One Participant with AE for N=250 Participants, with Varying Percentages of Participants with AEs.

	Category	95% CI ¹			Probability to Observe ≥ 1 Participant with AE (%) ²
		Lower Limit	Upper Limit	Width	
0.1%	Uncommon	0.00	1.67	1.67	22.1
1%	Common	0.17	3.17	3.00	91.9
10%	Very common	6.58	14.41	7.83	>99.9
50%		43.63	56.37	12.73	>99.9

1. Calculations done using SAS version 9.4 and validated using PASS (19) software.

2. Calculated using the binomial distribution.

CONFIDENTIAL

Phase IV Clinical Trial Protocol

GlaxoSmithKline
A phase IV trial of *Fluarix Tetra* in Indian
adults aged 65 years and older
Version 2.0, dated: 05 May 2023
Protocol/ Study No.: 218702
Page 52 of 74

[Table 7](#) shows 95% Clopper-Pearson CIs for the proposed N=250 and varying incidence of solicited/ unsolicited AEs. The AE incidences shown correspond to the categories uncommon ($\geq 1/1\,000$ to $<1/100$), common ($\geq 1/100$ to $<1/10$) and very common ($\geq 1/10$).

With N=250, the width observed for the 95% CIs is always $<13\%$, and for uncommon and common AEs it is $\leq 3\%$.

[Table 7](#) also shows, in the last column, the probability of observing at least 1 participant with AE. This probability is at least 91.9% for common and very common AEs.

CONFIDENTIAL

Phase IV Clinical Trial Protocol

 GlaxoSmithKline
 A phase IV trial of *Fluarix Tetra* in Indian
 adults aged 65 years and older
 Version 2.0, dated: 05 May 2023
 Protocol/ Study No.: 218702
 Page 53 of 74

Table 8. 95% Clopper-Pearson Exact Confidence Intervals and Probabilities to Observe at least One Participant with SAE for N=250 Participants, with Cumulative Incidence up to 1% Over a 6-month Period.

Months after Vaccination	Cumulative Incidence of SAE (%) ²	Clopper-Pearson 95% CI ¹			Probability to Observe ≥ 1 participant with SAE (%) ³
		Lower Limit (%)	Upper Limit (%)	Width	
1	0.17	0.00	1.79	1.79	34.1
2	0.33	0.00	2.09	2.09	56.6
3	0.50	0.02	2.38	2.35	71.4
4	0.67	0.06	2.65	2.59	81.2
5	0.83	0.11	2.91	2.80	87.7
6	1.00	0.17	3.17	3.00	91.9

1. SAS version 9.4 and validated using PASS (19) software.

2. Assuming linear increase in incidence from date of vaccination to 1% at 6 months.

3. Calculated using binomial distribution.

Table 8 shows 95% Clopper-Pearson CIs for 250 participants by cumulative incidence of SAE. The width of the 95% CIs is $\leq 3\%$ throughout. The probability of observing at least 1 participant with SAE is $>56\%$ for cumulative incidence from Month 2 onward [[Clopper 1934](#)].

Further details about the actual implementation of the Clopper-Pearson CIs will be provided in the Statistical Analysis Plan (SAP).

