3. BENEFIT/ RISK AND ETHICAL ASSESSMENT

The influenza virus is an important respiratory pathogen that causes annual epidemics and occasional pandemics. Virtually every year, epidemic influenza has a significant impact in terms of morbidity, mortality, and economic burden. Vaccination is presently the most effective way of controlling influenza and preventing its complications and mortality in persons at risk. Annual trivalent influenza vaccines (TIV) containing 2 A strains (H1N1 and H3N2) and 1 B-strain, which are intended to provide protection against influenza viruses that are expected to circulate in the upcoming season, have been used against seasonal influenza. However, since 1983, 2 antigenically and genetically distinct lineages of influenza B have co-circulated worldwide. As a consequence of the co-circulation of these 2 lineages, there is a certain degree of mismatch each season between the B-strain contained in the trivalent vaccine and the circulating B-strains. Since the 2 evolutionarily distinct lineages of influenza B virus continue to co-circulate, an additional B-strain antigen in the seasonal vaccine is expected to offer greater efficacy and broader protection. *Fluarix Tetra* is a quadrivalent influenza vaccine, comprising 2 A and 2 B-strains.

By participating in this study, the participant may benefit from being vaccinated with an inactivated quadrivalent influenza vaccine.

4. OBJECTIVES AND ENDPOINTS**Table 1. Study Objectives and Endpoints**

Objective(s)	Endpoint(s)/Estimand(s)
Primary	
• To evaluate reactogenicity and safety of Fluarix Tetra single dose 0.5 mL intramuscularly (I/M) in participants aged 65 years and above in India.	
• Number and percentage of subjects with solicited AEs (local as well as general) for 7 days from the date of vaccination (Day 1).• Number and percentage of subjects with unsolicited AEs starting from the date of vaccination for 21 days.• Number and percentage of subjects with SAEs from the date of vaccination for 21 days.
Secondary	

CONFIDENTIAL

Objective(s)	Endpoint(s)/Estimand(s)

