5. STUDY DESIGN

5.1 Study Description

Overview of study design: This trial is a prospective, multi-center, single-arm, open-label, Phase IV trial.

Study sites: This trial will be conducted in multiple sites during NH influenza season in India.

Study population: 250 participants aged 65 years and above in India will be enrolled.

Vaccination schedule: A single 0.5 mL I/M dose of *Fluarix Tetra* (NH 2023-2024) will be administered. The composition of the *Fluarix Tetra* (NH 2023-2024) vaccine is as follows:

A/Victoria/4897/2022 (H1N1) pdm09 - like strain* (A/Victoria/4897/2022, IVR-238)	15 micrograms HA**
A/Darwin/9/2021 (H3N2) - like strain* (A/Darwin/6/2021, IVR-227)	15 micrograms HA**
B/Austria/1359417/2021 – like strain* (B/Austria/1359417/2021, BVR-26)	15 micrograms HA**

CONFIDENTIAL

Phase IV Clinical Trial Protocol

GlaxoSmithKline
A phase IV trial of *Fluarix Tetra* in Indian
adults aged 65 years and older
Version 2.0, dated: 05 May 2023
Protocol/ Study No.: 218702
Page 28 of 74

B/Phuket/3073/2013 - like strain* (B/Phuket/3073/2013,
wild type) 15 micrograms HA**

per 0.5 mL dose

* propagated in fertilized hens' eggs from healthy chicken flocks

** HA - hemagglutinin

Safety and reactogenicity monitoring through the daily diary card:

- Recording of solicited AEs for 7 days after vaccination
- Recording of unsolicited AEs for 21 days after vaccination
- Recording of SAEs for 21 days after vaccination

Immunogenicity assessment:

- **Blood Samples:** Two 5 mL blood samples will be collected, one before administration of a single dose of trial vaccine at Day 1 and one at Day 22
- **Laboratory testing:** Serum HI titers will be measured against the 4 influenza strains *Fluarix Tetra* (NH 2023-2024) is designed to protect against (vaccine or vaccine-like strains). Geometric mean titers (GMT), seroconversion rate (SCR), MGI, and SPR will be evaluated to assess immunogenicity.

Duration of the trial: 22 days per participant.

Type of study vaccine intervention: Open-label.

Data collection:

Safety data - Trial participants will receive a diary card. The Investigator team will follow-up via a telephone call on Day 8 to assess participant's health status. The completed diary card will be collected on Day 22. The Investigator team will capture the data in an electronic case report form (eCRF). SAEs will be reported using the SAE Reporting Form.

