4.2.2. Main Analytical Approach

The primary endpoint analyses related to solicited AEs will be performed on the SSS. The primary endpoint analyses related to unsolicited AEs will be performed on the ES.

The number and percentage of participants reporting solicited administration-site AE (any, Grade 3, medically attended), systemic AE (any, Grade 3 or Grade 4, medically attended) and either administration-site or systemic AE (any, Grade 3, medically attended) during the follow-up period (Day 1 – Day 7) will be tabulated with exact Clopper-Pearson 95% CI.

The number and percentage of participants reporting at least 1 unsolicited AE (any, Grade 3, related, Grade 3 related, medically attended) classified by the Medical Dictionary for Regulatory Activities (MedDRA) during the 21-day follow-up period (Day 1 - Day 21) will be tabulated with exact 95% CI, overall and by MedDRA System Organ Class (SOC) and Preferred Term (PT).

The number and percentage of participants reporting at least 1 SAE (any, fatal, related, fatal related) during the trial period (Day 1 - Day 21) will be tabulated with exact 95% CI, overall and by MedDRA SOC and PT.

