5. SAMPLE SIZE DETERMINATION

Approximately 250 participants will be enrolled in this trial to achieve 200 evaluable participants considering that some participants may drop out of the study or some may not be included in data analysis due to missing or invalid data.

Table 2 95% Clopper-Pearson (exact) Confidence Intervals and probabilities to observe at least one participant with AE for N=250 participants, with varying percentages of participants with AEs.

		95% CI ¹			N = 250
	Category	Lower Limit (%)	Upper Limit (%)	Width (%)	Probability to observe ≥ 1 participant with AE (%) ²
0.1%	Uncommon	0.00	1.67	1.67	22.1
1%	Common	0.17	3.17	3.00	91.9
10%	Very common	6.58	14.41	7.83	>99.99
50%		43.63	56.37	12.73	>99.99

CI= confidence interval; AE= adverse event.

1. Calculations done using SAS version 9.4 and validated using Power and Sample Size (PASS) software [\(PASS, 2019\)](#).

2. Calculated using the binomial distribution.

Table 2 shows 95% Clopper-Pearson CIs for the proposed N=250 and varying incidence of solicited/ unsolicited AEs. The AE incidences shown correspond to the categories uncommon ($\geq 1/1\,000$ to $<1/100$), common ($\geq 1/100$ to $<1/10$) and very common ($\geq 1/10$).

With N=250, the width observed for the 95% CIs is always $< 13\%$, and for uncommon and common AEs it is $\leq 3\%$.

Table 2 also shows, in the last column, the probability of observing at least one participant with AE. This probability is at least 91.9% for common and very common AEs.

Table 3 95% Clopper-Pearson exact Confidence Intervals and probabilities to observe at least one participant with SAE for N=250 participants, with cumulative incidence up to 1% over a 6-month period.

Months after vaccination	Cumulative incidence of SAE (%)²	Clopper-Pearson 95% CI¹			Probability to observe ≥ 1 participant with SAE (%)³
		Lower Limit (%)	Upper Limit (%)	Width (%)	
1	0.17	0.00	1.79	1.79	34.1
2	0.33	0.00	2.09	2.09	56.6
3	0.50	0.02	2.38	2.35	71.4
4	0.67	0.06	2.65	2.59	81.2
5	0.83	0.11	2.91	2.80	87.7
6	1.00	0.17	3.17	3.00	91.1

1. Calculations done using SAS version 9.4 and validated using PASS ([PASS, 2019](#)) software.

2. Assuming linear increase in incidence from date of vaccination to 1% at 6 months.

3. Calculated using binomial distribution.

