Table 3 shows 95% Clopper-Pearson CIs for 250 participants by cumulative incidence of SAE. The width of the 95% CIs is $\leq 3\%$ throughout. The probability of observing at least 1 participant with SAE is $>56\%$ for cumulative incidence from Month 2 onwards ([Clopper CJ, 1934](#)).

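### The SAE precision tables run to 6 months, but SAEs are counted for 21 days, where the tables' own assumption gives about a 25–27% chance of seeing one

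*Protocol*

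**What the plan says.** The number and percentage of participants with SAEs is one of three primary endpoints. Protocol Section 4 (Table 1) defines it as "Number and percentage of subjects with SAEs from the date of vaccination for 21 days". SAP Section 4.2.2 says that SAEs "during the trial period (Day 1 - Day 21) will be tabulated with exact 95% CI". Protocol Section 5.1 gives the trial duration as "22 days per participant", and the Schedule of Activities puts the last visit at Day 22 (+3).

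The only precision tables specific to SAEs are Protocol Table 8 (Section 6.2) and SAP Table 3 (Section 5). The Protocol title ends "Participant with SAE for N=250 Participants, with Cumulative Incidence up to 1% Over a 6-month Period" and the SAP title ends "with cumulative incidence up to 1% over a 6-month period". Both tables have one row per month from Month 1 to Month 6. The footnote states the assumption: "Assuming linear increase in incidence from date of vaccination to 1% at 6 months". Below the tables, the one statement about detection is that the probability of at least one participant with an SAE exceeds 56% "for cumulative incidence from Month 2 onward" (Protocol) or "for cumulative incidence from Month 2 onwards" (SAP).

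**The concern.** No row of either table corresponds to the period over which SAEs are counted. The shortest row, Month 1, already runs past Day 21. The row chosen for comment, Month 2, lies well beyond the last visit.

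The trial answers a post-approval commitment on safety and immunogenicity in this age group, and all analyses are descriptive. Expected precision and detection probability are therefore the whole quantitative argument for its size. A regulator or ethics committee reading Section 6.2 would take away a better-than-even chance of observing an SAE. If the true chance under the same assumption is much lower, a count of zero could be over-read as reassurance when it was the expected outcome from the start.

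**Working it through.** **Inputs**
- N = 250 (Protocol Section 6.2). SAEs are analysed on the Exposed Set (Protocol Section 6.4.2; SAP Section 4.4.1.7), so 250 is the appropriate N if all enrolled participants are vaccinated.
- Cumulative SAE incidence: linear from 0 at vaccination to 1% at 6 months (footnote 2 of both tables).
- Detection probability: binomial, P(at least 1) = 1 − (1 − p)^250.
- Intervals: two-sided 95% Clopper-Pearson, evaluated at x = 250p, which need not be a whole number.
- SAE window: 21 days.

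**Step 1: reproduce Protocol Table 8.** With p = 1% × m/6 for month m:

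| Month | p (%) | P(at least 1), recomputed (%) | Protocol Table 8 (%) |
|---|---|---|---|
| 1 | 0.167 | 34.1 | 34.1 |
| 2 | 0.333 | 56.6 | 56.6 |
| 3 | 0.500 | 71.4 | 71.4 |
| 4 | 0.667 | 81.2 | 81.2 |
| 5 | 0.833 | 87.7 | 87.7 |
| 6 | 1.000 | 91.9 | 91.9 |

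The interval limits also match (Month 1: 0.00–1.79%; Month 6: 0.17–3.17%). The method is therefore not in doubt. SAP Table 3 prints 91.1 for Month 6, but the computed value is 91.89, and SAP Table 2 itself gives 91.9 for the same 1% and N = 250.

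**Step 2: apply the same method at 21 days.** The documents do not define the length of a month, so three conventions are shown:

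| 6 months taken as | p at 21 days | Expected participants with an SAE (250p) | P(at least 1) | 95% CI |
|---|---|---|---|---|
| 182.625 days | 1% × 21/182.625 = 0.1150% | 0.29 | 25.0% | 0.00–1.69% |
| 180 days | 1% × 21/180 = 0.1167% | 0.29 | 25.3% | 0.00–1.70% |
| 168 days | 1% × 21/168 = 0.1250% | 0.31 | 26.9% | 0.00–1.71% |

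P(no SAE) is the complement, 73.1–75.0%.

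**Step 3: sensitivity.**
- Counting to the latest permitted final visit (Day 25) with 6 months as 182.625 days gives p = 1% × 25/182.625 = 0.137% and P(at least 1) of about 29%. With 168 days, p = 0.149% and P is about 31%. Both stay below the Month 1 row.
- With 200 participants instead of 250, the 21-day probability would be 20.6–22.1%.

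**Step 4: what 56.6% in 21 days would require.** Solving 1 − (1 − p)^250 = 0.566 gives p = 0.333%. On the linear scale this is 0.333% × 182.625/21 = 2.9% at 6 months (0.333% × 168/21 = 2.7% with 4-week months), against the assumed 1%.

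**Step 5: what the trial can say whatever the assumption.** Exact 95% upper limits at N = 250 are 1.46% for 0 SAEs, 2.21% for 1 and 2.86% for 2.

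**The case against.** The best defence has four parts.

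1. **Low detection is disclosed elsewhere.** Protocol Table 7 has a 0.1% row (22.1%, CI 0.00–1.67%), close to the 21-day value. It covers solicited and unsolicited AEs, and the documents elsewhere count SAEs among unsolicited AEs. Section 6.4.6 says that the trial is poorly suited to detecting uncommon AEs, a band that includes 0.115%. This stands: the message is in the protocol. But neither place corrects the SAE-specific sentence, which a reader interested in SAEs will use.

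2. **The documents never claim 56% at 21 days.** The sentence is tied to Month 2, and Month 1 (34.1%) is printed. Against Month 1 the gap is only about 7 to 9 points. That is also true, but Month 1 still overstates, and the row singled out is one that no participant reaches.

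3. **The rows are valid functions of incidence and N; the month is only a label.** The probabilities do depend only on p and N, and the statement that interval widths are at most 3% survives (about 1.7% at 21 days). But the tables link p to time through an explicit assumption, so the label carries the meaning.

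4. **Nothing depends on it.** No hypothesis is tested, and the documents do not say that SAE detection determined N. This limits the consequence to a misleading justification. It does not make the justification right.

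**Conclusion.** The concern holds. The arithmetic in Protocol Table 8 is correct, but its horizon, and that of SAP Table 3, does not match the SAE endpoint. On the tables' own assumption, the chance of observing at least one participant with an SAE in the 21-day window is 25.0–26.9%, less than half the highlighted figure and below every printed row. The range reflects only the undefined month length. The result rests on N = 250 and on the linear rise to 1% at 6 months, for which Section 6.2 cites no source; a different assumption would give a different probability, but would not make Month 2 relevant. The 91.1 in SAP Table 3 is a misprint for 91.9.

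This should be corrected because it misdescribes what the trial can show on a primary safety endpoint. It does not affect the sample size, the conduct, the planned analysis or the inference after a zero count.

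**What to change.** In Protocol Table 8 and SAP Table 3:
- Replace the month-indexed rows with 21-day incidences for N = 250. Include the row implied by the stated assumption: about 0.115%, exact 95% CI about 0.00–1.69%, P(at least 1) about 25% (up to 0.125%, 0.00–1.71% and 26.9% with 4-week months; state the convention).
- If 0.17%, 0.33%, 0.50% or 1.00% are kept, label them as 21-day incidences and drop the months.
- Add the exact 95% upper limits for 0, 1 and 2 SAEs: 1.46%, 2.21% and 2.86%. These are attainable counts and need no incidence assumption.
- Delete the sentence about Month 2 in both documents. State instead that, under the linear assumption, the chance of at least one SAE in 21 days is about 25%.
- If the 1.00% row stays in the SAP, change 91.1 to 91.9.

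A smaller change, adding one 21-day row and rewording the sentence, would cure the main defect, but would leave rows for months that are not observed.

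The cost is a text and table revision of both documents. The protocol part needs a written amendment, handled under Section 7.7. The stated SAE detection figure becomes less favourable.
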